7.4.3 Laboratory Assessments

Standard laboratory assessments in this trial will consist of hematology, clinical biochemistry, and urinalysis panels: complete lists of parameters are presented in [Appendix B](#).

As an exogenous protein, sprifermin has the potential to trigger antibody formation, which could conceivably have safety, PK, or efficacy implications. Thus, subjects will be tested for binding and neutralizing antibodies to sprifermin/FGF-18. Only samples that are found to be positive for binding antibodies will be tested for neutralizing antibodies.

Blood, urine, and synovial fluid samples for laboratory assessment will be collected at the time points indicated in [Appendix E](#).

- Subjects are not required to fast before routine laboratory sample collection in this protocol, however, an 8-hour fast is required before blood or urine sample collection for biomarkers.
- For time points where IMP injections are administered, blood and urine samples will be collected pre-dose.
- For measurement of biomarkers in urine, second morning void samples should be obtained.
- Synovial fluid samples will be collected immediately before injection of the IMP as described in the MOP.

PK assessments are described in Section 7.5, and biomarker and PGt assessments are described in Section 7.6.

All laboratory assessments will be performed centrally. Instructions for sample collection, handling, and shipment are provided in the MOP.

Pregnancy Tests

For women of childbearing potential, pregnancy tests will be performed at the time points shown in [Appendix E](#) (during screening, before each injection of IMP, and at each visit involving X-ray and MRI). A serum test will be performed during screening, and urine tests will be performed at subsequent time points.

Management of Subjects with Laboratory Abnormalities

Laboratory abnormalities that Investigators consider to be clinically significant should be reported as AEs (see Section 7.4.1).

The best interest of the participating subject will always come before that of the trial. Abnormalities of any safety laboratory analysis considered to represent a significant danger to the subject will lead to immediate discontinuation of the drug, and the Medical Responsible must be informed immediately.

In the event of significant abnormalities considered not to represent a danger, continuation of the drug may be allowed after discussion with the Medical Responsible. These subjects will be followed up with appropriate medical management until there is a return to normal or baseline values, or until a clinical diagnosis of a trial-emergent illness is confirmed.

7.4.4 Vital Signs, Physical Examinations, and Other Assessments

Physical examinations and measurement of height, weight, and vital signs (sitting systolic and diastolic blood pressure, heart rate, and body temperature) will be performed at the time points specified in [Appendix E](#).

Standard 12-lead ECGs (reporting ventricular rate, PR, QRS, QT, and QTc intervals) will be obtained at the time points specified in [Appendix E](#). ECGs will be read centrally; procedures for transfer of data to the central reader are provided in the MOP. Original 12-lead ECG tracings will be retained in each individual subject's medical file. In case of abnormal results, a second original will be provided to the Sponsor. ECGs can be repeated at the discretion of the Investigator or co-Investigator.

One of the trial's safety endpoints is the incidence of AIRs, defined as increase of pain by 30 mm on a 100-mm VAS and a self-reported synovial fluid effusion (i.e., joint swelling) within 3 days following i.a. injection (see Section 7.4.1.1). Subjects will use trial diaries to record maximum levels of target knee pain experienced, using a 100-mm VAS, and presence or absence of joint swelling in the target knee. Completed diaries will be collected and reviewed at each visit, and information will be transcribed to the CRFs following medical review. AIRs will be identified by the Sponsor based on the information about pain and swelling transcribed from the diaries to the CRFs.

7.5 Pharmacokinetics

PK assessment will be performed for sprifermin/FGF-18 in serum and synovial fluid.

Sprifermin differs from the endogenous FGF-18 molecule in that it is truncated (i.e., it has 170 instead of 180 amino acids), it has a methionine extension, and it is not glycosylated.

Merck Serono internal Standard Operating Procedure HP01 describes the process for handling bioanalytical, PK, and pharmacodynamic (PD) data from double-blind clinical trials. To maintain

the blind for PK data during this trial, the randomization list will only be provided to the PK bioanalytical scientist or clinical trial team members after clinical database lock.

7.5.1 Body Fluids

Blood and synovial fluid samples for measurement of serum/synovial fluid sprifermin/FGF-18 levels will be collected at the time points indicated in the schedule of assessments in [Appendix E](#).

Detailed description of sample preparation, labels, and shipments will be given in the MOP. Details of the assays such as the validation procedure and definition of lower limit of quantification (LLOQ) will be described by the Sponsor/external laboratory in a separate analytical protocol. Some samples might be stored and used for additional analysis or for validation of new assays.

- Blood samples for the measurement of sprifermin/FGF-18 serum levels will be collected at pre-dose at Week 0 and thereafter at 2 hours after the last dose of each cycle.
- Synovial fluid for the measurement of sprifermin/FGF-18 levels will be aspirated under ultrasound guidance (32) prior to i.a. injection of sprifermin, as part of the i.a. injection procedure and using the same needle that will be used for IMP injection, as described in the MOP.

7.5.2 Pharmacokinetic Calculations

The PK analysis will be performed under the responsibility of the Sponsor according to the Sponsor's appropriate standard operating procedures. Sprifermin/FGF-18 serum and synovial fluid concentrations will be summarized at the time points shown in [Appendix E](#). Details of the analysis and data displays will be provided in the Statistical Analysis Plan (SAP). Analytes to be tested in this study will include serum and synovial fluid sprifermin/FGF-18.

7.6 Biomarkers and Pharmacogenetics

Circulating biomarkers will be assessed for all subjects in serum, urine, and (if sample volumes permit) synovial fluid. Exploratory PGt analyses will be performed only for subjects who provide separate informed consent.

7.6.1 Biomarkers to be Analyzed

Serological and urine biochemical markers of bone and joint tissue turnover will be evaluated. Potential biomarkers may include, but are not limited to: aggrecan chondroitin sulfate epitope 846 (CS846), II form of the propeptides from the N- terminus processed type II collagen (PIINP), propeptides from the C-terminus processed type II collagen (PIICP), and C-telopeptide cross-linking of type II collagen (CTX-II).

Measurement of biomarkers in synovial fluid is also foreseen. However, if the quantity of synovial fluid collected is not sufficient to permit both PK and biomarker measurement, priority will be given to PK.

Samples will be stored for up to 5 years after trial completion under the Sponsor's responsibility. During this time, it is possible that the samples will be re-analyzed by the Sponsor or its designee. This may include analyses for newly identified markers and/or a repeat of the original analysis with newer improved technologies. After this period of 5 years, either the samples will be destroyed or fully anonymized or new IEC/IRB approval will be requested to keep them for an additional period.

7.6.2 Body Fluids for Biomarker Assessment

Blood and urine samples for systemic biomarker assessment will be collected at the time points specified in [Appendix E](#). For time points where IMP injections are administered, samples will be collected pre-dose. For urine collection, second morning void samples should be obtained.

Synovial fluid samples will be collected at the time points specified in [Appendix E](#). These samples will be taken just before injection of the IMP as described in the MOP, as part of the i.a. injection procedure and using the same needle that will be used for IMP injection. If sample volume permits, biomarkers will be analyzed in the samples collected at Week 0/Visit 2, Week 28/Visit 9, Week 54/Visit 14 and Week 80/Visit 19; otherwise, priority will be given to PK.

Instructions for the preparation and handling of blood samples for assessment of circulating proteins can be found in the MOP.

7.6.3 Pharmacogenetics

Exploratory analyses are planned to identify potential associations of genetic variations with safety events, drug response, and/or treatment efficacy.

All subjects who are enrolled in the trial will be eligible to participate in the optional PGt analysis (except in countries where collection of PGt samples is not allowed). Participation is optional, and the subjects who choose to participate will need to sign a specific PGt ICF (see [Section 9.2](#)).

The results of the genetic analysis are for research purposes only. The results of the genetic tests will not be made available to the subject, members of his/her family, his/her personal physician, or other third parties, except as specified in [Section 9.3](#).

Once a subject has given appropriate consent, a single blood sample for PGt analysis will be collected; this sample can be taken at any trial visit (including pre-dose at the baseline visit).

Instructions for the preparation and handling of blood samples for PGt analysis can be found in the MOP.

Samples will be stored for up to 5 years after trial completion under the Sponsor's responsibility. During this time, it is possible that the samples will be re-analyzed by the Sponsor or its designee. This may include analyses for newly identified markers and/or a repeat of the original analysis with newer improved technologies. After this period of 5 years, either samples will be destroyed or fully anonymized or new IEC/IRB approval to keep the samples for an additional period will be requested.

7.7 Other Assessments

7.7.1 Knee Injury and Osteoarthritis Outcome Score - Quality of Life and Symptom Index Subscales

The KOOS (33) is a knee-specific questionnaire designed to evaluate both short-term and long-term consequences of knee injury, including OA; it is intended for use in knee injury potentially leading to post-traumatic OA or in primary OA. It consists of 42 items grouped into 5 subscales: pain, other symptoms (including swelling, restricted range of motion, and mechanical symptoms), function in daily living (ADL), function in sport and recreation (i.e., impact on more demanding physical activities), and impact on quality of life (including awareness of the knee condition and changes in lifestyle). The subscales are scored separately; each yields a score between 0 and 100, with 0 representing extreme knee problems and 100 representing absence of problems. The 42 items of the complete KOOS include the 24 items of the WOMAC Osteoarthritis Index (26), the most frequently used patient-assessed measure of treatment effect in OA. In this study, there will be no duplication of questions from the WOMAC and the KOOS.

The KOOS has been validated for use in patients undergoing total knee replacement for OA. Content validity in this patient group was assessed before surgery by asking patients to rate the importance of improvement in each of the KOOS subscales. Notably, larger effect sizes were seen with the KOOS compared to the WOMAC following TKR for severe knee OA (33),(34). A change of 10 points in KOOS score has been proposed as representing clinically meaningful difference based on experience with the WOMAC; however, the minimal perceptible clinical improvement (MPCI; defined as the change in score associated with the smallest change in health status detectable by the patient) has not been formally assessed for the KOOS (33).

In this trial, the KOOS quality of life subscale will be evaluated at the same time points as the WOMAC, as a complement to the more general MOS SF-36 (see below). The KOOS Symptom Index will also be completed at the same time points for correlation with the other indicators of tibiofemoral cartilage loss (e.g., MRI, X-ray).

7.7.2 Medical Outcomes Study Short Form-36 General Health Survey

The MOS SF-36 (version 2.0) is a multi-purpose questionnaire that measures general health status and QOL, is not knee specific, and is the single PRO measure included to assess the overall status of the patient. It consists of 36 items that evaluate 8 dimensions of health: physical function, bodily pain, general mental health, vitality (energy and fatigue), social function, physical role (role limitations due to physical health), emotional role (role limitations due to

personal or emotional problems), and general health perceptions. Scores for the 8 dimensions/subscales range from 0 to 100, with higher scores representing better QOL. The MOS SF-36 is a generic measure as opposed to one targeting a specific age group, disease, or treatment. Accordingly, it has proven useful in surveys of general and specific populations, comparing the relative burden of different diseases, and examining the health benefits associated with a wide range of treatments. It should be noted that there is no defined MOS SF-36 score that represents a healthy, unimpaired condition. A subject with no disease symptoms would not necessarily have subscale scores of 100 or corresponding physical, mental, and summary scores of 400 or 800.

According to the User's Manual for the MOS SF-36 v. 2.0 Health Survey and Kosinski et al. (35), "minimal important differences" in MOS SF-36 scores consist of changes of 2 to 4 points, depending on the subscale concerned.

7.7.3 Measure of Intermittent and Constant Osteoarthritis Pain Questionnaire

The ICOAP (36),(37),(38) is an 11-item questionnaire for assessment of pain in subjects with OA that considers both constant and intermittent experiences of pain. Questions address the frequency and severity of pain and its impact on the subject's QOL (including sleep and emotional distress).

The ICOAP is designed to be responsive to change in pain over time and with treatment. Subjects are asked to respond to the questionnaire considering their symptoms over the past week, taking into consideration any pain medication that they may be using (i.e., to report their experience of pain while taking the medication).

The ICOAP yields a total pain score that can range from 0 to 44 points, a constant pain subscore that can range from 0 to 20 points, and an intermittent pain subscore that can range from 0 to 24 points; higher scores indicate more severe, frequent, or distressing pain.

7.7.4 Patient Global Impression of Change

Global impression scales (39) are recommended for use in chronic pain clinical trials as a core outcome measure of global improvement with treatment relative to baseline symptoms (40). It provides a responsive and readily interpretable measure of participant's assessments of the clinical importance of their improvement or worsening over the course of the clinical trial.

The PGIC used in this trial is based on the IMMPACT recommendations (40) and will assess the subject's global improvement since starting study treatment using a 7-point scale:

“Since getting the first injection of study treatment in your knee how would you describe the change in overall symptoms for this knee:”

- 1 = very much improved
- 2 = much improved
- 3 = minimally improved
- 4 = no change
- 5 = minimally worse
- 6 = much worse
- 7 = very much worse

7.7.5 11-Point Numerical Rating Scale Pain Score

The subject will indicate the worst pain in past 24 hours in the target and contralateral knee using an 11-point NRS. The NRS for pain is a patient-reported unidimensional pain scale recommended for assessing pain intensity (41) which is frequently used instrument in pain trials, and also in subjects with osteoarthritis.

The NRS is scaled from 0 (no pain) to 10 (worst possible pain). It has good validity, reliability, and sensitivity, being similar in sensitivity to a 100-mm VAS when comparing postoperative pain intensity (42).

In this protocol, the NRS will be used as a supplementary pain scale to the WOMAC. The NRS has a 24-hour recall period, which may be preferable for detecting recent changes in health status compared to PRO questionnaires with longer recall periods (43). Also, the NRS involves a single overall question whereas the WOMAC uses a group questions to characterize different aspects of knee pain.

7.7.6 Pain in Other Joints

Data on the presence of pain in ‘other’ joints (that is, joints other than the knee) will be obtained because, like pain in the contralateral knee, pain in other joints could potentially become a confounding variable when assessing self-reported activities of daily living (WOMAC ADL), physical functioning during the 20-meter walk test, and overall health-related quality of life (MOS SF-36). Pain in other joints may also serve as indicator of overall OA progression. As has been recommended for use in OA studies (44), a scale model of the human body (homunculus) will be used (see Appendix F). During subject interview, the homunculus, with circles in six bilateral joints (shoulder, elbow, wrist, hand/finger, ankle, foot) and neck, for a total of 13 joints, will be shown to subjects to indicate painful joints.

8 Statistics

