In addition to the WOMAC, multiple questionnaires will be used to explore the treatment effect on the symptoms associated with OA. The Symptom Index subscale of the KOOS, a knee-specific questionnaire described in Section 7.7.1, will be used to assess symptoms associated with tibiofemoral cartilage loss. Pain, a major component of OA, will additionally be assessed using an 11-point NRS, evaluating the worst knee pain in the past 24 hours (Section 7.7.5). In addition, the ICOAP questionnaire will be used to explore the effect of treatment on intermittent and continuous OA pain (Section 7.7.3). Both of these assessments will complement the WOMAC pain index score.

Pain in other joints may be a confounding variable in the assessment of self-reported activities of daily living (WOMAC ADL), performance on the 20-meter walk test, and overall health-related quality of life (MOS SF-36). Pain in other joints may also serve as indicator of overall OA progression. Pain in the non-target knee will be assessed using the same 11-point NRS used in the target knee. In addition, pain in joints other than the knees will be identified using a scale model of the human body (homunculus; Section 7.7.6).

The PGA and PGIC will be used to capture the subject's global impression of their target knee pain and measure global improvement with treatment relative to baseline symptoms. As described in Sections 7.7.3 and 7.7.4, these are responsive and readily interpretable measures of participant's assessments of the clinical importance of their improvement or worsening over the course of the clinical trial.

Evaluation of JSW by X-ray

Change in joint space narrowing will be visualized with the "fixed flexion" knee radiograph protocol ((21); see Section 7.3.4).

Among rheumatologists, determination of joint space narrowing by X-ray is considered to be a semi-quantitative method for assessment of progression of knee OA. This outcome is recognized as valid by regulatory authorities in Europe and the USA (20),(22).

Evaluation of Safety

AE monitoring, safety laboratory measurements, measurement of vital signs, weight, physical examinations, ECGs, incidence of surgery, and, in case of a non-systemic drug, assessment of local tolerability are standard measures to evaluate the safety profile of an investigational product. Safety endpoints to be assessed in this trial are consistent with those used in previous studies with sprifermin.

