7.1.3.1 Baseline Visit (Week 0; Visit 2)

The baseline visit must take place within 42 days after the beginning of screening, following the pain medication washout necessary for confirmation of trial eligibility (see Section 5.4).

The following procedures will be performed at the baseline visit before administration of IMP. Subject questionnaires (WOMAC, PGA, KOOS QOL, KOOS Symptom Index, NRS pain score in the target and contralateral knee, pain in other joints, MOS SF-36, and ICOAP) should be completed before any other procedures are performed; the WOMAC should be completed first.

- WOMAC (see [Appendix C](#))
- PGA (see [Section 7.3.3](#))
- KOOS QOL (see [Appendix D](#))
- KOOS Symptom Index (see [Appendix D](#))
- NRS pain (see [Section 7.7.5](#))
- Pain in other joints (see [Appendix F](#))
- MOS SF-36 (see [Appendix C](#))
- ICOAP (see [Appendix C](#))
- Review of AEs and concomitant medications (see [Sections 7.4.1](#) and [6.5](#))
- Review of subject diaries (see [Section 7.1.1](#))
- Vital signs measurement (see [Section 7.4.4](#))
- Sample collection for hematology, biochemistry, and urinalysis (see [Section 7.4.3](#) and [Appendix B](#))
- Blood collection for testing for antibodies to sprifermin/FGF-18 (see [Section 7.4.3](#))
- Blood collection for PK analysis (see [Section 7.5.1](#))
- Blood collection (fasting) for biomarker analysis (see [Section 7.6.2](#))
- Blood collection for optional PGt analyses (for subjects who have signed the PGt informed consent). If a blood sample cannot be obtained at the baseline visit, this sample can be taken at any subsequent visit (see [Section 7.6.3](#)).
- Urine collection (second morning void) for biomarker analysis (see [Section 7.6.2](#))
- Urine pregnancy test for women of childbearing potential
- 20-meter walk test (see [Section 7.3.5](#))
- Target knee MRI (see [Section 7.3.1](#))
- Review of inclusion and exclusion criteria (see [Sections 5.3.1](#), [5.3.2](#), and [5.4](#))
- Randomization

Provided that the subject fulfills all inclusion and no exclusion criteria, s/he will be randomized to treatment using the IVRS as described in [Section 6.3](#). Medication from the assigned treatment kit will be prepared as described in [Section 6.2](#) and administered i.a. according to instructions in the MOP.

- Using aseptic technique, i.a. administration of IMP will be guided by ultrasound to ensure delivery of the IMP into the joint space.

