8.5.3 Analysis of Secondary Endpoints

Descriptive statistics for secondary efficacy endpoints will be presented by time point (visit) and treatment group.

The same ANOVA model used for the primary endpoint will be used to assess the treatment effect on continuous secondary endpoints such as MRI endpoints, WOMAC endpoints (total, pain, function, and stiffness scores), and X-ray endpoints at each time point and over time.

Logistic regression will be used to assess the treatment effect on the binary efficacy endpoints such as the OMERACT-OARSI responder rate. Point estimates for each pairwise comparison and corresponding 95% CIs and p-values will be provided.

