Appendix E: Schedule of Trial Procedures

Table 5 Schedule of Trial Procedures for Visits 1 to 11

Visit	Screening ⁽¹⁾		Baseline	V3	V4	V5	V6	V7	V8	V9	V10	V11	
	V1a	V1b	V2										
Week ⁽²⁾	-42 to -4 days		0 ⁽³⁾	1	2	3	12	26	27	28	29	38	
Informed consents ⁽⁴⁾	X												
Demographics	X												
Medical/medication history	X												
Inclusion/Exclusion criteria	X	X	X										
Withdraw analgesia prior to visit ⁽⁵⁾		X	X				X	X				X	
Identification of target knee		X											
Randomization				X									
WOMAC (question 1 only)	X	X											
WOMAC (full questionnaire)			X				X	X				X	
Patient's Global Assessment	X		X				X	X				X	
KOOS QOL and Symptom Index			X				X	X				X	
PGIC							X	X				X	
Pain NRS both knees	X	X	X				X	X				X	
Pain in other joints			X					X					
MOS SF-36			X					X					
ICOAP			X				X	X				X	
AEs	Continuous												
Concomitant medications	Continuous												
Surgical procedures (target knee)	Continuous												
Review of subject diaries		X	X	X	X	X	X	X	X	X	X	X	X
Vital signs ⁽⁶⁾		X		X	X	X	X	X	X	X	X	X	X
Physical examination ⁽⁷⁾		X					X	X					
ECG		X											
Clinical laboratory specimens ⁽⁸⁾		X		X				X					
Antibodies to sprifermin/FGF-18				X		X		X			X		
PK serum collection ⁽⁹⁾				X		X					X		
Biomarker serum collection ⁽¹⁰⁾				X							X		
Biomarker urine collection				X							X		
PGt sample collection ⁽¹¹⁾	One sample needed. Can be obtained at any trial visit, preferably at baseline.												
Pregnancy test ⁽¹²⁾		X		X	X	X			X	X	X		
20-meter walk test		X	X					X	X			X	
Knee X-ray(s) ⁽¹³⁾⁽¹⁴⁾		X											
Target knee MRI ⁽³⁾⁽¹⁴⁾				X				X					
Synovial fluid collection ⁽¹⁵⁾				X	X	X		X	X	X			
i.a. injection of IMP				X	X	X		X	X	X			

Table footnotes appear on following page.

Abbreviations: AEs: adverse events; ECG: electrocardiogram; i.a: intra-articular; ICOAP: Measure of Intermittent and Constant Osteoarthritis Pain; KOOS: Knee Injury and Osteoarthritis Outcome Score; MRI: magnetic resonance imaging; NRS: numerical rating scale; PGIC: Patient Global Impression of Change; PK: pharmacokinetic; QOL: quality of life; WOMAC: Western Ontario and McMaster Universities Osteoarthritis Index

Subjects will be requested to discontinue the intake of any pain medications for at least 5 half-lives before a visit involving completion of the WOMAC.

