ANOVA models are used for several endpoints. For each endpoint all available time-points except LOCF (specified in table 3) should be included and summarized. The general model specification for model that include 4 post-baseline measurements (i.e. qMRI) in SAS will be:

```
proc mixed data=p3 method=reml;
  class grpn vs usubjid CNTRGR1N ;
 model &var. = grpn vs grpn*vs base CNTRGR1N / solution;
  repeated vs / subject=usubjid type=&type. r;
  lsmeans grpn / adjust=dunnett diff=control('1') cl;
  lsmeans grpn*vs / adjust=dunnett diff=control('1' 'Week 26') cl;
  lsmeans grpn*vs / adjust=dunnett diff=control('1' 'Week 52') cl;
  lsmeans grpn*vs / adjust=dunnett diff=control('1' 'Week 78') cl;
 lsmeans grpn*vs / adjust=dunnett diff=control('1' 'Week 104') cl;
  lsmeans grpn*vs / slice=vs;
  contrast 'Linear trend (overall)' grpn -2 -1 0 1 2;
  contrast 'Linear trend at Week 26' grpn -2 -1 0 1 2 grpn*vs -2 0 0 0 -1 0 0
0 0 0 0 0 1 0 0 0 2 0 0 0;
  contrast 'Linear trend at Week 52' grpn -2 -1 0 1 2 grpn*vs 0 -2 0 0 0 -1 0
0 0 0 0 0 0 1 0 0 0 2 0 0;
  contrast 'Linear trend at Week 78' grpn -2 -1 0 1 2 grpn*vs 0 0 -2 0 0 0 -1
0 0 0 0 0 0 0 1 0 0 0 2 0;
  contrast 'Linear trend at Week 104' grpn -2 -1 0 1 2 grpn*vs 0 0 0 -2 0 0 0
-1 0 0 0 0 0 0 0 1 0 0 0 2;
```

run;

12 Disposition of Subjects and Discontinuations

This section presents specifications for reporting subject disposition and treatment/trial discontinuations. Additionally, procedures for reporting protocol deviations are provided.

Subject disposition will be presented for all subjects and by treatment group in terms of:

- Total number of subjects screened (i.e. subjects who signed informed consent)
- Number and percentages of subjects discontinuing the trial prior to randomization divided by main reason for discontinuation (did not meet all eligibility criteria, withdrew consent, other), by country and site, and overall.
- Number and percentages of randomized subjects.
- Number and percentages of exposed subjects
- Number and percentages of randomized subjects who completed the DBPC treatment phase. For the 2-year analysis a completer is a subject with no date of study discontinuation before day 819.
- Number and percentages of randomized subjects who discontinued the trial after randomization, during DPBC i.e. before day 819, and during extended follow up phase (grouped by treatment) and main reason (AE, death, lost to follow-up, etc).

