The WOMAC total score, and absolute changes from baseline in the WOMAC total score for the target knee will be presented with summary statistics for all timepoints (including baseline, post-treatment, and LOCF).

Absolute change from baseline in WOMAC total score over 2 years will be considered a continuous variable and will be analysed using a model similar to the ANOVA model used for the primary endpoint.

If an entire questionnaire is missing for a time point, no imputations will be performed for that time point. If some items are missing, imputation for Total score (and for sub scores) will be performed using same principal used for KOOS.

WOMAC Sub Scores

WOMAC sub scores (weight-bearing pain score (sum of items: walking, going up and down stairs, and standing), pain, function and stiffness) will be tabulated descriptively as described above for Total score.

Absolute change from baseline in pain, function, stiffness, and weight-bearing pain, over 2 years will be analysed using a model similar to the ANOVA model described under primary endpoint.

WALK test

Time needed to complete the 20-meter walk tests as well as absolute change from baseline will be presented with summary statistics per timepoint (including LOCF). No imputation for missing data will be done. Absolute change from baseline in time needed to complete the 20-meter walk will be analysed using a model similar to the ANOVA model described under primary endpoint.

Patient Global Assessment (PGA)

The Patient Global Assessment is based on subject's answer to the question "Considering all the ways your osteoarthritis of the knee has affected you during the last 48 Hours, select the number that best describes the impact of your knee osteoarthritis on your daily life", and can take on values between 0-10 (0=None, 10=Extreme), for summaries the values are rescaled to 0-100 by multiplication with 10.

The Patient Global Assessment will be presented with summary statistics per timepoint (including LOCF) as well as absolute change from baseline. Mean score will be presented as described for continuous variables, and also number and percentages per score will be presented. No imputation for missing data will be done (except LOCF).

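### WOMAC function and 20-meter walk models leave out baseline contralateral-knee and other-joint pain, which the protocol flags as possible confounders: a modest, cheap gain in precision is missed

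*Protocol*

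**What the plan says.** Protocol Section 5.2 states: "Pain in other joints may be a confounding variable in the assessment of self-reported activities of daily living". It adds the walk test and the SF-36 to the list. Section 7.7.6 repeats the reasoning and puts contralateral-knee pain on the same footing: "like pain in the contralateral knee, pain in other joints could potentially become a confounding variable when assessing self-reported activities of daily living".

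Both variables are available at baseline. The schedule in Protocol Appendix E has a row "Pain NRS both knees", marked at screening and at Visit 2. Section 7.1.3.1 lists pain in other joints among the pre-dose baseline procedures. Section 7.7.6 describes a body map of 13 sites.

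For the analysis, Protocol Section 8.5.3 says: "The same ANOVA model used for the primary endpoint will be used to assess the treatment effect on continuous secondary endpoints". The general model in SAP Section 11 (ANOVA models) is "model &var. = grpn vs grpn*vs base CNTRGR1N / solution", that is, arm, visit, arm by visit, the endpoint's own baseline and pooled country. SAP Section 16.2 applies a similar model to the WOMAC total and sub scores. For the walk it says: "Absolute change from baseline in time needed to complete the 20-meter walk will be analysed using a model similar to the ANOVA model".

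Elsewhere in the SAP the two pain measures are only tabulated: other-joint pain in the baseline tables (Section 13.3), and both in exploratory summaries by arm and visit (Section 16.5). A bilateral/unilateral subgroup exists (Section 10), but it is defined by X-ray and is descriptive.

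**The concern.** Only one knee is treated, while the walk and many daily activities depend on both legs and on other joints. Variation from untreated joints that the endpoint's own baseline does not capture stays in the error term. A chance baseline imbalance between an active arm and placebo also stays in the estimated difference.

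The design does not control these variables. Randomization is stratified by country only (Protocol Section 8.2), bilateral OA is admitted (Section 7.2), and no exclusion criterion limits pain in the other knee or elsewhere.

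WOMAC function is where this matters most. Section 5.2 expects any symptom benefit to show more clearly there than in pain or stiffness, and its lowest planned power, 53%, is the lowest in Table 3 of Section 8.1.

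**Working it through.** **Inputs.** Protocol Section 8.1, Table 3: n = 76 evaluable per group, SD 21 for normalized WOMAC function, differences of 7, 9 and 10 points, stated power 53%, 75% and 83%. Table 3 gives no alpha, so 5% two-sided is assumed, as stated for the primary tests. The documents do not give the partial correlation r between the outcome and the two baseline pain variables, beyond own baseline. I assume 0, 0.1, 0.2 and 0.3.

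**Step 1: reproduce the plan's figure.** SE of a pairwise difference = 21 × sqrt(2/76) = 3.41 points. At 7 points the noncentrality is 7/3.41 = 2.05. The noncentral t with 150 df gives 53.3%. At 9 and 10 points it gives 74.7% and 83.1%. All three agree with Table 3.

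**Step 2: precision after adjustment.** The residual SD becomes 21 × sqrt(1 − r²). The 95% CI half-width is 1.96 × 3.41 × sqrt(1 − r²).

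| r | SE reduction | CI half-width (points) | Power at 7 points | Power at 10 points |
|---|---|---|---|---|
| 0 | 0% | 6.68 | 53.3% | 83.1% |
| 0.1 | 0.5% | 6.64 | 53.7% | 83.4% |
| 0.2 | 2.0% | 6.54 | 54.9% | 84.5% |
| 0.3 | 4.6% | 6.37 | 57.2% | 86.4% |

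**Step 3: chance imbalance.** A 2-SE baseline imbalance is 2 × sqrt(2/76) = 0.32 SD of the covariate. The resulting shift in the unadjusted difference is 0.324 × r × 21, which is 0 / 0.7 / 1.4 / 2.0 points for r = 0 / 0.1 / 0.2 / 0.3. In units of the SE of the difference this is 2r, or 0 / 0.2 / 0.4 / 0.6. By simulation, at least one of the four active-placebo pairs shows an imbalance beyond 2 SE, in either direction, with probability about 14%. That is the chance of the imbalance, not of a misleading result.

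These shifts are upper values. Here r is defined given the endpoint's own baseline, but it is multiplied by the full SD of 21. If 21 is the SD before baseline adjustment, which the documents do not say, the shifts are smaller.

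**Step 4: is the gap filled elsewhere?** Protocol Section 8.5.2 promises a sensitivity analysis on the influence of covariates, but only for the MRI primary endpoint. The SAP Section 16.1 paragraph headed for fixed effects and covariates contains only a rank analysis of cartilage thickness. Neither covers WOMAC function or the walk.

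No equivalent calculation is possible for the walk, because the documents give no SD or planned difference for it.

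**The case against.** **A reader might infer that the symptom comparisons are confounded. The documents do not support that.** Both protocol statements are hedged: such pain may be, or could become, a confounder. In a randomized comparison a baseline covariate causes no systematic bias, and the unadjusted SE and type I error already allow for chance imbalance. This stands in full.

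**A reader might also infer that no symptom model anywhere uses these variables. That cannot be verified.** Protocol Section 8.5.5 plans exploratory pharmacometric modeling of WOMAC with a covariate analysis, under a separate plan that was not supplied. That work is exploratory and does not produce the secondary-endpoint estimates, so it does not replace a covariate in SAP Section 16.2.

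**The gain may be small.** Baseline WOMAC and baseline walk time are measured in the presence of the same other-joint pain, so the own-baseline term already absorbs part of the effect. At r = 0 nothing is gained. Even a 2.0-point shift is 0.6 SE and lies well inside a CI of about ±6.7 points. This stands, and it limits the point to a modest improvement.

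**Other steps exist.** The knee-specific WOMAC form (Section 7.3.2) is meant to reduce contralateral confounding, and baseline other-joint pain will be tabulated. But the form does not address other joints and cannot apply to the walk. A table shows an imbalance without correcting for it.

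**The covariate is imperfect.** Nine of the 13 map sites are shoulder, elbow, wrist, hand/finger or neck. Only ankles and feet are lower limb, and hips are absent. The data are also collected to follow OA progression, so they are not wasted as planned. Both remarks are fair. The first is a reason to expect a small r.

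**Conclusion.** The point holds as a cheap improvement. The protocol singles out two variables as possible confounders of WOMAC function and the walk and collects them before dosing. The SAP models for those endpoints, and its sensitivity analyses, then leave them out.

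For an assumed r of 0 to 0.3, the cost of leaving them out is 0 to about 4 percentage points of power at 7 points (53% against 53–57%). The exposure to a 2-SE imbalance is at most about 0 to 2.0 points. Both ranges rest on the assumed r and on the Table 3 SD of 21.

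This is neither a bias nor an arithmetic error. Table 3 reproduces, the primary MRI analysis is unaffected, and own baseline plus the stratification factor is a defensible model. The case for acting is that adjustment chosen after an imbalance has been seen would be open to challenge, whereas prespecified adjustment would not.

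**What to change.** In SAP Section 16.2, before unblinding, specify the PROC MIXED models for WOMAC function and the 20-meter walk with two added Visit 2 covariates: contralateral-knee NRS pain (0–10) and the count of painful other-joint sites (0–13).

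- Use baseline values only. Later pain may be affected by treatment and should not be conditioned on.
- State a simple rule for missing covariate values, because PROC MIXED otherwise drops that subject's records.
- Leave the cartilage models unchanged. WOMAC pain and stiffness need no change, since the protocol does not name them in this context. The SF-36 is named, but it has no model in the SAP to amend.

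The cost is a short addition to the SAP, two terms in existing code and two degrees of freedom. No new data are needed. If the covariates turn out not to be prognostic, nothing is gained.
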